1.0 Background

Torsades de pointes (TdP) is a life-threatening ventricular arrhythmia associated with heart rate-corrected QT (QTc) interval prolongation, which can be caused by > 150 commonly prescribed drugs. TdP risk is higher in women than men, and is modulated by progesterone, which shortens the QTc interval, and estradiol, which lengthens it. The higher the serum progesterone and the progesterone:estradiol ratio, the lower the risk of QTc interval prolongation and TdP. The TdP risk in women increases with age, likely due to declining postmenopausal serum progesterone concentrations. Methods to reduce TdP risk in older women requiring therapy with QTc interval-prolonging drugs have not been developed. In addition, differential effects of progesterone on drug-induced lengthening of early vs late ventricular repolarization in humans are unknown.

■■■ Drug-Induced QTc Interval Prolongation and Torsades de Pointes (TdP).

QTc interval prolongation may result in TdP, which is associated with sudden cardiac death.¹ We propose to investigate a novel approach to minimizing drug-induced QTc interval lengthening in postmenopausal women: oral progesterone administration. Over 150 available drugs may cause TdP,² including antimicrobials, antidepressants, antipsychotics, antiarrhythmics, methadone, and others. Many QTc interval -prolonging drugs are among the top 200 drugs prescribed in the U.S. and millions of patients are exposed annually to drugs that cause TdP.³ Methods to reduce the TdP risk in high-risk patients have not been developed; risk reduction strategies are critically needed. The investigation described herein will determine the efficacy of a novel therapeutic approach to attenuate drug-induced QTc lengthening in postmenopausal women.

■■■ Female Sex as a Risk Factor for QTc Interval Prolongation/TdP.

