Progesterone enhances I_{Ks} current (influencing late phase repolarization)⁷ and decreases I_{Ca,L} density in rabbit cardiomyocytes¹⁶ (early repolarization). Progesterone may also activate the (PI3K/AKT) signaling pathway,¹⁷ inhibiting late sodium current (early repolarization). However, the effects of progesterone on drug-induced lengthening of specific phases of ventricular repolarization in humans are unknown, though this information carries important clinical significance. If progesterone attenuates drug-induced lengthening of both early and late repolarization, then it can be anticipated to attenuate QTc lengthening induced by drugs that lengthen early or late repolarization (or both). However, if progesterone is effective for attenuation of drug-induced lengthening of only early or late repolarization, but not both, then progesterone may be effective for attenuation of QTc lengthening induced by drugs that inhibit only early

repolarization (late sodium activating agents, PI3K inhibitors) or late repolarization (I_{Kr} inhibitors). We will assess progesterone's influence on early and late repolarization by measuring its effect on ibutilide-associated lengthening of $J-T_{peak}$ and $T_{peak}-T_{end}$ in both proposed clinical studies.

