Specific Aim 1: Determine the efficacy of oral progesterone as a preventive method to diminish drug-induced QT interval lengthening in postmenopausal women. *Hypothesis:* Oral progesterone attenuates drug-induced QTc interval response in postmenopausal women. Postmenopausal women will receive progesterone in a prospective, randomized, double-blind, placebo-controlled 2-way crossover study. QTc interval response to ibutilide will be assessed.

Specific Aim 2: Determine the influence of oral progesterone on drug-induced lengthening of early versus late ventricular repolarization in postmenopausal women. *Hypothesis:* Based on preclinical data reporting effects of progesterone on the slow delayed rectifier potassium (I_{Ks}), and L-type calcium ($I_{Ca,L}$) current, progesterone attenuates drug-induced lengthening of both early (represented by measurement of J-Tpeak) and late (represented by measurement of Tpeak-Tend) ventricular repolarization in postmenopausal women.

Specific Aim 3: Determine the efficacy of oral progesterone to diminish drug-induced QTc interval lengthening in premenopausal women during the ovulation phase of the menstrual cycle, when serum estradiol concentrations are high. *Hypothesis:* Despite higher serum estradiol, oral progesterone achieves a sufficiently high progesterone: estradiol ratio to attenuate drug-induced QTc interval response in premenopausal women during the ovulation phase.

Specific Aim 4: Determine the influence of oral progesterone on drug-induced lengthening of early versus late ventricular repolarization in premenopausal

women during the ovulation phase of the menstrual cycle, when serum estradiol concentrations are high. Hypothesis: Based on preclinical data reporting effects of progesterone on the slow delayed rectifier potassium (I_{Ks}), and L-type calcium ($I_{Ca,L}$) current, progesterone attenuates drug-induced lengthening of both early (represented by measurement of J-Tpeak) and late (represented by measurement of Tpeak-Tend) ventricular repolarization in premenopausal women during the ovulation phase.

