8.0 Statistical Considerations

Statistical analysis will be performed separately for the two subject populations:

- Postmenopausal women (progesterone vs placebo)
- Premenopausal women (progesterone vs placebo)

QT intervals will be corrected for heart rate using two correction methods, the Fridericia (QT_F) and Framingham (QT_{Fra}) methods.

Study Endpoints: Comparison of progesterone and placebo phases for: 1) Baseline (pre-ibutilide) maximum QT_F & QT_{Fra} 2) Ibutilide effect on maximum QT_F & QT_{Fra}, 3) Ibutilide effect on maximum % change in QT_F & QT_{Fra}, and 4) Ibutilide effect on AUEC_{0-1.17} and AUEC_{0-8.17}. Endpoints will be correlated with progesterone concentrations. 5)

Statistical analyses: Means (standard deviations) or medians (interquartile range) will be presented for continuous variables. Distribution normality will be assessed using the Kolmogorov-Smirnov test. Paired t-test (if normality holds) or signed-rank test (if normality does not hold) will be used to compare outcome measures between the two treatment phases; 95% confidence intervals will be calculated. SAS 9.4 (Cary, NC) will be

used. Correlations between the primary endpoints and serum progesterone concentrations will be performed using Pearson's correlation coefficient.

Anticipated Outcomes: During the progesterone phase, the following outcome measures will be significantly lower than vs placebo: 1) Pre-ibutilide QT_F and QT_{Fra}; 2) Post-ibutilide maximum QT_F and QT_{Fra}; 3) AUEC 1 hour and 8 hours after ibutilide; 4) Post-ibutilide % change in maximum QT_F and QT_{Fra}, 5) J-T_{peak} and T_{peak-T_{end}}.

Sample Size Calculation: In this 2-way crossover study, at a two-sided α level of 0.05 and a power of 0.80, a sample size of 20 subjects in the postmenopausal population and n=20 subjects in the premenopausal population will be sufficient to detect a difference in maximum QT_F and QT_{Fra} of 15 ms, assuming a QT_F and QT_{Fra} interval prolongation of 24±12 ms associated with ibutilide in the absence of progesterone.

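### Aims 2 and 4 ask about early versus late repolarization, but only separate tests of J-Tpeak and Tpeak-Tend are planned; these can support an effect on both, not a conclusion that only one is affected

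*Combined protocol and SAP*

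**What the plan says.** The question is framed as a comparison. Section 1.0 names the gap: "differential effects of progesterone on drug-induced lengthening of early vs late ventricular repolarization in humans are unknown". In section 2.0, Aim 2 is "Determine the influence of oral progesterone on drug-induced lengthening of early versus late ventricular repolarization in postmenopausal women", and Aim 4 asks the same in premenopausal women in the ovulation phase.

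The hypothesis under both aims is that "progesterone attenuates drug-induced lengthening of both early (represented by measurement of J-Tpeak) and late" repolarization (Tpeak-Tend) are affected.

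Section 1.0, on early and/or late repolarization, also considers the alternative: "if progesterone is effective for attenuation of drug-induced lengthening of only early or late repolarization, but not both". It then links an early-only effect to one set of drugs (late sodium activating agents, PI3K inhibitors) and a late-only effect to another (IKr inhibitors).

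Section 8.0 plans, separately in each population, a paired t-test or a signed-rank test, depending on a normality check, which "will be used to compare outcome measures between the two treatment phases", with 95% confidence intervals. The two phases here are progesterone and placebo. J-Tpeak and Tpeak-Tend appear in that section only as the fifth anticipated outcome, in a list introduced by "the following outcome measures will be significantly lower than vs placebo". No comparison of the two effects is described, and no rule covers a result where one interval is significant and the other is not.

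**The concern.** A significant result on one interval and a non-significant result on the other do not show that the two effects differ. Nor does p > 0.05 in 20 women show that an effect is absent. If the separate tests split, the plan offers nothing else on which to base a statement that progesterone acts on one phase only. According to the Background, that statement would point to the QT-prolonging drugs against which progesterone may help. A split that arose by chance could therefore carry weight in two of the four aims.

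**Working it through.** **1. The plan's own figure.** Section 8.0 gives 20 women per population for a 15 ms difference in maximum QTc, SD 12 ms, two-sided alpha 0.05, power 0.80. The two-group normal formula gives 2 × (1.960 + 0.842)² × 12² / 15² = 2 × 7.849 × 0.64 = 10.05 per group, and power with 10 per group is 0.798. So 20 is close to a parallel-group total. For the planned paired t-test, 8 women suffice if the SD of the paired difference is 12 ms, and 13 if it is 12 × √2 = 16.97 ms (correlation 0). All of this concerns maximum QTc. No effect, SD, correlation or power is given for J-Tpeak or Tpeak-Tend, so what follows rests on assumptions and is shown as ranges.

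**2. How often two separate tests split by chance.** Assumptions: n = 20, two-sided 0.05, paired t-tests, the same true standardised effect (mean paired difference divided by its SD) on both intervals. With noncentral t, power of 50%, 80% and 90% corresponds to standardised effects of 0.462, 0.660 and 0.764. If the two estimates are independent, P(exactly one significant) = 2p(1 − p): 2 × 0.5 × 0.5 = 50%, 2 × 0.8 × 0.2 = 32%, 2 × 0.9 × 0.1 = 18%. Simulation gives the other correlations:

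| Power per test | corr −0.5 | 0 | +0.5 | +0.8 |
|---|---|---|---|---|
| 50% | 64% | 50% | 34% | 21% |
| 80% | 38% | 32% | 23% | 15% |
| 90% | 20% | 18% | 14% | 9% |

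The sign of the correlation is not known. The shared T-peak landmark pushes it negative; a common response to ibutilide or progesterone pushes it positive.

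**3. Error of a direct contrast.** For each woman, take her progesterone-minus-placebo effect on one interval minus that on the other, and apply a one-sample t-test. When the two true effects are equal on the scale analysed, this rejects 5% of the time. Equal *standardised* effects are equal in ms only if the SDs are equal. With SD ratio k and correlation r, the standardised contrast in ms is d(k − 1)/√(1 + k² − 2rk). At d = 0.660 and k = 2:

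- r = 0: 0.660/√5 = 0.295, rejection 24%.
- r = +0.5: 0.660/√3 = 0.381, rejection about 37%.

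In those cases the ms effects do differ, but neither is absent. A contrast that excludes zero is therefore necessary for a claim of *only early* or *only late*, but not sufficient.

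**4. Power of the contrast at n = 20.** Assume one interval has 80% power alone, the other has no effect, and SDs are equal. The standardised contrast is 0.660/√(2(1 − r)).

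| Correlation | Standardised contrast | Power |
|---|---|---|
| −0.5 | 0.381 | 37% |
| 0 | 0.467 | 51% |
| +0.5 | 0.660 | 80% |

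**The case against.** The strongest reply is that the hypothesis under Aims 2 and 4 is attenuation of both intervals. For that, two separate tests that must both be significant are valid, and no contrast is needed. This stands, and it limits the point to selectivity.

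A reader might also infer that the protocol commits to treating p > 0.05 on one interval as no effect. It does not say so. The Background passage is conditional and speaks of what may follow if the true effect is confined to one phase. The misreading is a risk left open by the lack of any rule for a split result, not a written plan.

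The planned 95% confidence intervals help, because they show whether a non-significant interval is still compatible with an effect. But they are per interval, and since both come from the same women, the CI of the difference cannot be derived from them without the correlation.

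The endpoint list in section 8.0 ends with an empty fifth item, which may be text lost in extraction. The point is therefore limited to the text that can be read. The paragraph on statistical analyses appears complete.

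Finally, the split rates depend on assumed power and correlation. With strong positive correlation they fall to 9-21%, so it would go too far to say that a selective conclusion would usually be wrong.

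**Conclusion.** The point holds in a limited form. The planned tests can establish that progesterone attenuates lengthening of both intervals. They cannot establish that it acts on one and not the other, although the aims and Background raise that possibility and attach drug-class implications to it. Given 20 women, equal standardised effects and 50-90% power per test, a chance split arises in about 9-64% of trials per population (correlation +0.8 to −0.5), and in 32% at 80% power and zero correlation. None of these inputs for the two intervals is in the documents, so the range should be read as an illustration of the risk.

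Two stronger readings are not supported. One is that Aims 2 and 4 cannot be answered: their stated hypothesis can be tested as planned. The other is that the trial is underpowered for the intervals: the documents do not allow that power to be calculated. This is a cheap improvement to interpretation, not a flaw in the design.

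**What to change.** Add to section 8.0, within each population:

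1. For each woman, compute the progesterone-minus-placebo effect on the ibutilide-induced lengthening of J-Tpeak and of Tpeak-Tend. Report the paired difference between the two effects with a 95% CI.
2. Fix one scale in advance, for example % change, with ms as supportive. The choice matters because effects that are equal on one scale need not be equal on another.
3. Claim *only early* or *only late* only if the CI of the contrast excludes zero **and** the CI for the other interval excludes a pre-specified meaningful effect.
4. Otherwise report both effects with their CIs, and state that p > 0.05 will not be read as no effect.

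The cost is one extra contrast per population on measurements already planned, plus agreement on the scale and on the smallest meaningful effect. The downside is limited power, about 37-80% at n = 20 under the assumptions in step 4 of the working. Selectivity will be claimed less often, and the contrast should be presented as an estimate. No change in sample size is needed.

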9.0 Privacy/Confidentiality Issues

All ECGs will be collected using a standard ECG machine, on which the ECG data are collected on paper. This information will not contain the patients' names, just an unique identifier. Blood samples will be collected and maintained in a locked laboratory freezer, they will not contain the patients' names, just an unique identifier. Medical information, such as laboratory and echocardiogram information will be stored on a password protected computer database containing only an unique identifier. All information linking the patient's name and health information to the unique identifier will be stored in a locked cabinet in the study coordinator's office. All this information will not be stored electronically. Information on the password protected computer database will only be accessed by the investigators. All information with unique identifiers will be locked in the study coordinator's office or laboratory, or on a password protected computer. To assure study coordinator's office is physically secure, it is located on the 3rd floor of the FTB Faculty Office Building at Eskenazi Medical Center, which requires authorized entry. Furthermore, the study coordinator's office remains locked and any information that can be used to identify patients will be kept in a locked cabinet and not stored electronically. All study documentation will be stored for a minimum of seven years after completion of the study. All paper documentation will be shredded and electronic files deleted.

There will be paper copies of spreadsheet for the purpose of statistical analysis, pharmacokinetic and pharmacodynamic analysis shared with the co-investigators involved in the analysis, however, the unique identifier will be the only information that is available on the spreadsheets. The information linking the unique identifier to the patient will be kept in a locked cabinet in the study coordinator's office.

Safeguards used to protect the confidentiality and security of health information

Any information that is gathered about these patients will be kept confidential and any information that is generated on a patient will does not ultimately participate in the study will be destroyed immediately.

All ECGs will be collected using digital ECG recordings. Information entered will not contain the patients' names, just a unique identifier. Blood samples will be collected and maintained in a locked laboratory freezer, they will not contain the patients' names, just a unique identifier. Medical information, such as laboratory information will be stored on a password protected computer database containing only a unique identifier. All information linking the patient's name and health information to the unique identifier will be stored in a locked cabinet in [name] office. All this information will not be stored electronically. Information on the password protected computer database will only be accessed by the investigators. All information with unique identifiers will be locked in the study coordinator's office or laboratory, or on a password protected computer. To assure the study coordinator's office is physically secure, it is located on the 3rd floor of the FTB Faculty Office Building at Eskenazi Medical Center, which requires authorized entry. Furthermore, the study coordinator's office remains locked and any information that can be used to identify patients will be kept in a locked cabinet and not stored electronically. All study documentation will be stored for a minimum of seven years after completion of the study. All paper documentation will be shredded and electronic files deleted.

There will be paper copies of spreadsheet for the purpose of statistical analysis and will be shared with the co-investigators involved in the analysis, however, the unique identifier will be the only information that is available on the spreadsheets. The information linking the unique identifier to the patient will be kept in a locked cabinet in the study coordinator's office.

Discuss the methods for ensuring participant privacy, and the methods for protecting privacy and confidentiality.

Muenster man Tomaselli E, Tisdale JE, et al. Circulation 2018 (abstract: in press)	n=14, randomized 3-way crossover (n=42 doses of ibutilide 0.003 mg/kg)	Men \geq 65 years of age	0/42									
Tisdale JE, et al. Circulation 2018 (abstract; in press)	n=20, randomized parallel (n=20 doses of ibutilide 0.003 mg/kg)	n=10 subjects with HFpEF n=10 matched control subjects	0/20									
Total in all studies			0/151 0% incidence at dose used in our studies	0/252	1/42	0/2	2/40	20/852 (2.3%)	2/152 (1.3%)	1/42 (2.4%)	10/371 (2.7%)	36/1,904 (1.9%)

*patients with torsades had reduced LVEF

¶This patient had NYHA class II HF with decreased LVEF

§These 2 patients had NYHA class III HF with LVEF 45% and NYHA class II HF with LVEF 30%

‡both patients had LVEF < 20%

Other data:

Gowda, et al - Am J Ther 2002 – 4 cases of ibutilide-induced TdP – two doses of 1.0 mg (n=3), one dose of 1.0 mg (n=1)

Investigators' Experience Administering Intravenous (IV) Ibutilide 0.003 mg/kg

In our studies to date, we have administered n=118 doses of IV ibutilide 0.003 mg/kg to study volunteers. This has resulted in:

- n=0 occurrences of torsades de pointes
- n= 0 occurrences of ventricular tachyarrhythmias of any kind
- n=2 (1.7%) instances of transient QTc interval > 500 ms. In both cases, the QTc interval declined to < 500 ms within a couple of minutes, and rapidly declined to < 450 ms shortly thereafter
